7.4.3 Ophthalmic Examinations

Subjects are required to have a standard ophthalmology exam performed by an ophthalmologist at the time points indicated in the Time and Event Table (Section 7.1). The exam will include best corrected visual acuity, tonometry, slit lamp biomicroscopic examination, visual field examination, and dilated indirect fundoscopy with special attention to retinal abnormalities. Optical coherence tomography is strongly recommended at scheduled visits, and if retinal abnormalities are suspected. Other types of ancillary testing including color fundus photography and fluorescein angiography are also recommended if clinically indicated. Refer to Section 8.2.7 for additional details on management of visual changes.

7.4.4 Vital Signs

Vital sign measurements will include systolic and diastolic BP, temperature, pulse rate and respiratory rate. Vital signs will be measured at the time points indicated in the Time and Event Table (Section 7.1). Vital signs may be measured more frequently if warranted by the clinical condition of the subject.

- Vital sign measurements to be measured in semi-supine position after 5 minutes rest
- Three readings of BP and pulse rate should be taken. The first reading should be rejected and the second and third readings averaged to give the measurement to be recorded in the eCRF.

Refer to Section 8.1.1.3.1 and Section 8.1.1.3.2 for guidance on the monitoring and management of hypertension.

If subject develops a fever, refer to Section 8.2.3 for management guidelines for pyrexia. Refer to the SPM for details regarding measurement of vital signs.

7.4.5 Performance Status

The performance status will be assessed using the ECOG performance status scale (Appendix 1).

7.4.6 Electrocardiogram

Electrocardiograms (12-Lead ECGs) will be obtained using an ECG machine that automatically calculates heart rate and measures PR, QRS, QT, and QTc intervals. At each assessment, a 12-lead ECG will be performed by qualified site personnel after the subject has rested at least 5 minutes in a semi-recumbent or supine position.

Those QTc values >480 msec as calculated by the machine must be confirmed manually using Bazett's formula given below:

$$QTcB = QT \times (1/\sqrt{RR})$$

If there are any clinically significant abnormalities including, but not limited to, a QTcB >500 msec, confirm with two additional ECGs taken at least 5 minutes apart.

As of Protocol Amendment 11, transmission of ECGs to a central storage facility is discontinued. For all new ECGs obtained, two copies of the ECG tracings should be obtained at the time of the ECG; the first copy will be kept in the subject's medical chart and the second copy will be kept in the study file for retrospective collection by the sponsor if necessary.

Refer to Section 8.1.1.1 for QTc withdrawal criteria and additional QTc readings that may be necessary.

7.4.7 Echocardiogram

Echocardiograms (ECHOs) will be performed to assess cardiac ejection fraction and cardiac valve abnormalities. ECHOs will be performed at the time points indicated in the Time and Event Table (Section 7.1). The evaluation by the echocardiographer should include an evaluation for LVEF and both right and left-sided valvular lesions.

The procedure (ECHO) to document the subject's baseline LVEF status must be used consistently throughout the study. If possible, it is also preferred that interpretation of LVEF status be performed consistently by the same reviewer throughout the study. Copies of all ECHOs performed on ALL subjects will be required by the sponsor for review. Instructions for submission of ECHOs are provided in the SPM.

7.4.8 Clinical Laboratory Assessments

General laboratory assessments and histology-specific laboratory assessments will be required during the study and should be performed by a local laboratory. Laboratory tests may be done 7 days prior to the scheduled visit in order to have results available for review by investigator prior to the scheduled visit date.

Urine tests for protein/creatinine may be done up to 3 days prior to the scheduled visit date. If a 24-hr urine collection for protein has been completed within 5 days prior to scheduled visit date, a urine sample for protein/creatinine is not necessary.

If additional non-protocol specified laboratory assessments are performed at the institution's local laboratory and result in a change in subject management or are considered clinical significant by the investigator (i.e., AE, SAE or dose modification) the results must be recorded in the subject's eCRF.

All laboratory tests with values that are significantly abnormal during study participation or within 28 days after the last dose of study treatment(s) should be repeated until the values

return to within normal range or baseline. All subjects who have a Grade 3 or 4 laboratory abnormality at time of study withdrawal must be followed until resolution to Grade 2 or less, unless it is unlikely to improve due to underlying disease. If such values do not return to within normal range within a period judged reasonable by the investigator, the etiology should be identified and the Medical Lead notified.

Laboratory requisition forms must be completed and samples must be clearly labeled with the subject number, protocol number, site/center number, and visit date. Refer to the lab manual for appropriate processing and handling of samples to avoid duplicate and/or additional blood draws.

Refer to [Appendix 17](#) for an estimation of the volume of blood samples collected during the study.

Table 6 Clinical Laboratory Assessments

Hematology

RBC Count	RBC Indices (at Screening and if hemoglobin decreases ≥ 2 g/dL compared to baseline):	Automated WBC Differential:
Platelets	MCV MCH MCHC Reticulocyte Count	Lymphocytes Monocytes Eosinophils Basophils
WBC Count (absolute)		
Hemoglobin		
Hematocrit		
Absolute neutrophil count (ANC)		

Clinical Chemistry

BUN	Potassium	Total Protein	Total and direct bilirubin ¹
Creatinine ³	Chloride ²	Phosphorus	AST
Glucose	Uric Acid ²	Magnesium	ALT
Sodium	Calcium	LDH	Alkaline Phosphatase
Albumin	HbA1c ⁶	GGT	

Coagulation

PT
PTT
INR

Urinalysis⁴

Color	Specific gravity	Ketones	Urobilinogen
Appearance	Glucose	Blood	
pH	Protein ⁵	Leukocyte esterase	

Other Tests

Amylase and lipase [monitor via local laboratory when clinically indicated to evaluate certain AEs (i.e., abdominal pain, pancreatitis, etc.)]
Serum or urine β -hCG ⁶
For subjects with a history of chronic HBV and/or HCV, the following tests will be performed at Screening: 
 • Viral hepatitis serology; • Hepatitis B surface antigen and Hepatitis B core antibody (IgM); and/or • Hepatitis C RNA

Abbreviations: ALT, alanine aminotransferase; ANC, absolute neutrophil count; AST, aspartate aminotransferase; β -hCG, Beta-human chorionic gonadotropin; BUN, blood urea nitrogen; GGT, gamma glutamyl transferase; INR, international normalization ratio; HbA1C, hemoglobin A1C; HBV, hepatitis B virus; HCV, hepatitis C virus; LDH, lactate dehydrogenase; MCV, mean corpuscular volume; MCH, mean corpuscular hemoglobin; MCHC, mean corpuscular hemoglobin concentration; PT, prothrombin time; PTT, partial thromboplastin time; RBC, red blood cells; TSH, thyroid stimulating hormone; ULN, upper limit of normal; WBC, white blood cells

1. Direct bilirubin is required only if the total bilirubin is elevated (≥ 2 times the ULN)
 2. Chemistry evaluation of chloride or uric acid is not required where there are logistical constraints.
 3. If serum creatinine is >2.0 mg/dL, calculate creatinine clearance using standard Cockcroft-Gault method ([Appendix 3](#)).
 4. If urine protein result is not available, urine albumin result may be used.
 5. For female subjects of childbearing potential only, unless subject has had a hysterectomy, undergone a tubal ligation within 1 year prior to Screening or has been post-menopausal for at least 1 year prior to Screening.
- HbA1c testing to be performed every 12 weeks (+/-3 days)

7.4.8.1 Additional Histology Specific Assessments and Histology Confirmation

For ATC Cohort ONLY: Thyroid stimulating hormone (TSH) and Free T4: Serum TSH suppression (lowering TSH below the LLN) through the use of thyroid hormone replacement (e.g., levothyroxine) should be considered prior to the first dose of study treatment and throughout the study. However, the decision to suppress TSH is optional and dependent upon the investigator weighing the risk and benefits for each individual subject. If the investigator is unsure about suppressing the TSH, it is recommended that an endocrinologist be consulted. Free T4 will also be evaluated.

For NSGCT/NGGCT Cohort ONLY: β -HCG and AFP: These laboratory assessments will be completed as indicated in the Time and Event Table (Section 7.1).

For BTC and ASI Cohorts ONLY: CEA and CA19-9: These laboratory assessments will be completed as indicated in the Time and Event Table (Section 7.1).

Histology Confirmation for ATC and WHO Grade 1-4 Glioma Cohorts ONLY:

A tissue specimen from the biopsy of a primary or metastatic site must be submitted to a Novartis designated central reference laboratory as soon as possible after enrollment for possible retrospective confirmation of histologic type. Refer to the SPM and the Lab Manual for details regarding sample submission.

7.4.9 Monitoring for Non-Cutaneous Secondary/Recurrent Malignancy

Prior to initiation of treatment subjects should undergo a head and neck examination with minimally visual inspection of oral mucosa and lymph node palpitation, as well as chest/abdomen CT scan. Subjects should be monitored as clinically indicated during treatment and for up to 6 months after treatment discontinuation or until a new anti-cancer therapy is initiated. Anal examinations and pelvic examinations (for women) are required before and at the end of treatment or when considered clinically indicated. Complete blood cell counts should be performed as clinically indicated. Abnormal findings should be managed according to standard clinical practice.

Any new non-cutaneous secondary/recurrent malignancy should be reported as an SAE and treated according to standard clinical practice.

7.4.10 Pregnancy Testing and Reporting

7.4.10.1 Pregnancy Testing

The need for a screening pregnancy test depends on whether a female subject is of childbearing or non-childbearing potential.

A female of non-childbearing potential (i.e., physiologically incapable of becoming pregnant) is defined as any female who has had a hysterectomy, bilateral oophorectomy (ovariectomy) or bilateral tubal ligation, or is post-menopausal defined as 1 year without menses with an appropriate clinical profile, e.g., age appropriate, >45 years in the absence of hormone replacement therapy (HRT). In questionable cases, the subject must have a follicle stimulating hormone (FSH) value >40 mIU/mL and an estradiol value <40 pg/mL (<140 pmol/L).

A female of child-bearing potential is defined as any female who does not meet the criteria of non-childbearing potential as described in the previous paragraph.

If a female subject is of childbearing potential, she must have a serum β -HCG pregnancy test performed within 7 days prior to the first dose of study treatment. Subjects with a positive pregnancy test result must be excluded from the study. Subjects with a negative pregnancy test result must agree to use a highly effective contraception method (see Section 9.1) during the study and for 16 weeks following discontinuation of trametinib when taken in combination with dabrafenib, or for 2 weeks following discontinuation of dabrafenib monotherapy.

7.4.10.2 Pregnancy Reporting

Any pregnancy that occurs during study participation must be reported using a clinical trial pregnancy form. To ensure subject safety, each pregnancy must be reported to the sponsor within 24 hours of learning of its occurrence. The pregnancy must be followed up to determine outcome (including premature termination) and status of mother and child. Pregnancy complications and elective terminations for medical reasons must be reported as an AE or SAE. Spontaneous abortions must be reported as an SAE. Any SAE occurring in association with a pregnancy brought to the investigator's attention after the subject has completed the study and considered by the investigator as possibly related to the study treatment, must be promptly reported to the sponsor.

7.4.10.3 Time period for collecting pregnancy information

All pregnancies in female subjects and/or female partners of male subject will be collected after the start of dosing until the follow-up visit.

7.4.10.4 Action to be taken if pregnancy occurs in a female partner of a male study subject

The investigator will attempt to collect pregnancy information on any female partner of a male study subject who becomes pregnant while participating in this study. The investigator will record pregnancy information on the appropriate form and submit it to the sponsor within 24 hours of learning of the partner's pregnancy. The partner will also be followed to determine the outcome of the pregnancy. Information on the status of the mother and child will be forwarded to the sponsor. Generally, follow-up will be no longer than 6 to 8 weeks following the estimated delivery date. Any premature termination of the pregnancy will be reported.

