19. **PREGNANCY TEST:** Perform only in female subjects of childbearing potential.
 20. **PREGNANCY TEST:** A **serum** pregnancy test should be performed no more than 7 days prior to the first dose of study treatments.
 21. **PREGNANCY TEST:** A **serum or urine** pregnancy test will be performed every 8 weeks during the first 48 weeks of study treatment, then every 12 weeks thereafter, and at the Follow-up Visit.
 22. **MONITORING for NON-CUTANEOUS SECONDARY/RECURRENT MALIGNANCY:** During study treatment, monitor as clinically appropriate which may include a head/neck exam every 3 months and a chest/abdominal CT scan or MRI every 6 months.
 23. **MONITORING for NON-CUTANEOUS SECONDARY/RECURRENT MALIGNANCY:** This assessment is to be part of the physical exam and should include visual inspection of the oral mucosa and lymph node palpation.
 24. **MONITORING for NON-CUTANEOUS SECONDARY/RECURRENT MALIGNANCY:** Following discontinuation of study treatments, monitoring (which may include a chest/abdominal CT scan or MRI) should continue for up to 6 months or until initiation of new anti-cancer therapy.
 25. **DISEASE ASSESSMENTS (Solid Tumor Cohorts only):** See Section 7.5.1 for details on baseline and post-baseline disease assessments for the solid tumor cohorts: ATC, ASI, BTC, GIST, NSGCT/NGGCT and WHO Grade 1-4 Glioma.

26. **DISEASE ASSESSMENTS (Solid Tumor Cohorts only):** Baseline disease assessments must be performed within 28 days prior to enrollment (or within 35 days if MRI is used for disease assessment).
27. **DISEASE ASSESSMENTS (Solid Tumor Cohorts only):** Disease assessments are every 8 weeks during the first 48 weeks of study treatment, then every 12 weeks thereafter unless otherwise noted, and at the Follow-up Visit. Confirmatory scan(s) are to be performed ≥ 28 days after documented CR or PR. If subject discontinues treatment for reasons other than disease progression, disease assessments should continue every 12 weeks until disease progression, initiation of new anti-cancer treatment, subject withdrawal of consent, or death.
28. **HISTOLOGY CONFIRMATION: (ATC and WHO grade 1-4 cohorts only)** A tissue specimen for possible retrospective histology confirmation should be obtained and submitted to a Novartis designated central reference laboratory. Please refer to the SPM for the requirements of the tissue specimen that is required for the histology confirmation.

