45. **PK Sampling - Week 8, Week 12, and Follow-up Visit:** A single 2 mL blood sample for PK analysis of trametinib, dabrafenib and its metabolites (hydroxy-dabrafenib and desmethyl-dabrafenib) will be collected at Week 8 (pre-dose), Week 12 (pre-dose), and at the Follow-up Visit. Subjects with morning clinic visits are to be instructed to withhold their morning doses of study treatment and PK samples will be collected prior to dabrafenib administration. Subjects with afternoon clinic visits are to be instructed to take their morning doses as usual and PK samples will be collected 4 to 8 hrs following dabrafenib administration. **Samples at the Follow-up Visit are no longer requested for collection as of Protocol Amendment 11.**

[REDACTED]

- 
54. **STUDY TREATMENT:** Subjects must receive their supply of study treatments within 3 days of enrollment.
55. **FOLLOW-UP VISIT:** The Follow-up Visit should take place within 28 days (+7 days) of the last dose of study treatments. If the subject is unable to return to clinic, site staff is encouraged to call subject for assessment of AEs.
56. **FOLLOW-UP VISIT:** All safety and laboratory assessments should be performed unless the assessments were performed within 4 weeks prior to the Follow-up Visit.
57. **FOLLOW-UP VISIT:** If the last cardiac assessment was >12 weeks prior to the Follow-up Visit, an ECHO should be performed.
58. **EXTENDED FOLLOW-UP:** The following evaluations will be performed for all patients in all cohorts.
- a) Dermatologic exam. Exams will be performed every 4 weeks (+/-7 days) for the first 6 months. The skin will be carefully examined and pictures and biopsy will be taken of any new or changed skin lesions.
 - b) If study treatments are permanently discontinued prior to the subject having confirmed disease progression, the subject will continue to have disease assessments every 12 weeks (+/-14 days) until disease progression or initiation of new anti-cancer treatment, or death, whichever comes first.
 - c) Subjects will be followed every 12 weeks (+/-14 days) for survival until the subject dies or withdraws consent or is lost to follow up, or up to a time period as defined in Section 16.3. Survival follow up may be performed via clinic visit, a telephone contact, an email or by mail. The initiation of any new anti-cancer treatment(s) and date of last contact should also be documented.

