9 LIFESTYLE AND/OR DIETARY RESTRICTIONS

9.1 Contraception Requirements

9.1.1 Female Subjects

Women of child-bearing potential, defined as all women physiologically capable of becoming pregnant, must use highly effective methods of contraception during dosing and for 16 weeks after stopping treatment.

Highly effective contraception methods include:

- a. Total abstinence (when this is in line with the preferred and usual lifestyle of the subject). Periodic abstinence (e.g., calendar, ovulation, symptothermal, post-ovulation methods) and withdrawal are not acceptable methods of contraception.
- b. Female sterilization (have had surgical bilateral oophorectomy with or without hysterectomy), total hysterectomy, or tubal ligation at least six weeks before taking study treatment. In case of oophorectomy alone, only when the reproductive status of the woman has been confirmed by follow up hormone level assessment.
- c. Sterilization (at least 6 months prior to screening) for male partners. The vasectomized male partner should be the sole partner for that subject.
- d. Placement of a hormonal or non-hormonal intrauterine device (IUD) or intrauterine system (IUS) with a documented failure rate of less than 1% per year.

Notes:

- a. Double-barrier contraception: condom and occlusive cap (diaphragm or cervical/vault caps) with a vaginal spermicidal agent (foam/gel/cream/suppository) are not considered highly effective methods of contraception.
- b. Hormonal based methods (e.g. oral contraceptives) are not considered as highly effective methods of contraception due to potential drug-drug interactions with dabrafenib and/or trametinib (see Section [10.2](#)).
- c. Women are considered post-menopausal and not of child bearing potential if they have had 12 months of natural (spontaneous) amenorrhea with an appropriate clinical profile (i.e. age appropriate, history of vasomotor symptoms) or have had surgical bilateral oophorectomy (with or without hysterectomy), total hysterectomy, or tubal ligation at least six weeks ago. In the case of oophorectomy alone, only when the reproductive status of the woman has been confirmed by follow up hormone level assessment is she considered not of child bearing potential.

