9.1.2 Male Subjects

Male subjects (including those that have had a vasectomy) must use a condom during intercourse while taking dabrafenib and/or trametinib treatment. Once dabrafenib and trametinib are both permanently discontinued, the patient must use a condom for 16 weeks after the last dose of the study treatments. The patient should not father a child during the study treatment period or during the specified time frames after discontinuation of study treatment.

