16.4 Subject Completion

A subject is considered to have discontinued the study if the subject is lost to follow-up or withdraws consent or another reason exists that prevents additional data from being collected on the subject.

A subject is considered to have completed the study if they die while receiving study treatment(s) or during the extended follow-up period. The cause of death should be documented in the eCRF.

Data collection will continue until a subject has completed or discontinued the study.

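### Pregnancy collection ends at the follow-up visit, 11 to 12 weeks short of the 16-week post-treatment contraception period, and conflicts with the duty to report any pregnancy during participation

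*Protocol*

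**What the plan says.** Protocol Section 7.4.10.3 is the only place that expressly sets the period for collecting pregnancy information. For female subjects and female partners of male subjects, pregnancies "will be collected after the start of dosing until the follow-up visit". Footnote 55 of the Time and Event Table (Section 7.1) fixes that visit: "The Follow-up Visit should take place within 28 days (+7 days) of the last dose of study treatments".

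The contraception period is longer. Section 9.1.1 opens by saying that women of child-bearing potential "must use highly effective methods of contraception during dosing and for 16 weeks after stopping treatment". Section 7.4.10.1 has a two-part rule for women: "for 16 weeks following discontinuation of trametinib when taken in combination with dabrafenib, or for 2 weeks following discontinuation of dabrafenib monotherapy". The later text of 9.1.1 repeats the two-part rule. For men, Section 9.1.2 says that "the patient must use a condom for 16 weeks after the last dose of the study treatments", with no monotherapy exception.

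Two other clauses point to a later end of reporting. Section 7.4.10.2 says: "Any pregnancy that occurs during study participation must be reported using a clinical trial pregnancy form". Section 16.4 says: "A subject is considered to have completed the study if they die while receiving study treatment(s) or during the extended follow-up period", and has data collection run until the subject completes or discontinues the study.

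**The concern.** Section 1.4 reports embryofetal toxicity, including teratogenic effects, in animal studies of both drugs, and the protocol asks for contraception well beyond the last dose. One would expect pregnancy collection to last at least as long as the contraception requirement. The clause that sets the collection period stops at the first post-treatment visit instead.

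Nothing scheduled after that visit looks for a pregnancy. Footnote 21 of the Time and Event Table places the tests every 8 weeks for the first 48 weeks, "then every 12 weeks thereafter, and at the Follow-up Visit"; no test follows. Footnote 58 lists the extended follow-up assessments (skin, disease, survival and new therapy, head and neck, optional imaging), and pregnancy is not among them. Routine adverse event collection ends 30 days after treatment (Section 11.7).

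At stake is the completeness of safety information on pregnancies that begin after treatment but within the contraception period. The point does not touch the efficacy endpoints, the sample size or the error rates.

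**Working it through.** The documents give no pregnancy count or rate, so there is no plan figure to reproduce. The check is interval arithmetic, followed by a comparison of the clauses.

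**Inputs**
- Contraception period after the combination (women, Section 7.4.10.1) and after the last dose (men, Section 9.1.2): 16 weeks = 16 × 7 = 112 days.
- Contraception period for women after dabrafenib monotherapy (Section 7.4.10.1): 2 weeks = 14 days.
- End of the collection window (Section 7.4.10.3 with footnote 55): day 28, or day 35 at the latest.

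**Uncovered time = contraception period − day of follow-up visit**
- Visit on day 28: 112 − 28 = 84 days = 12 weeks; 84/112 = 75.0%.
- Visit on day 35: 112 − 35 = 77 days = 11 weeks; 77/112 = 68.8%.
- A visit before day 28 leaves more uncovered.
- Women after dabrafenib monotherapy, 14-day rule: 0 days uncovered if the visit is on day 14 or later.

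**Sensitivity to the monotherapy exception.** The documents do not say how many women end on dabrafenib alone. Let s be that share, assumed between 0 and 50%, and v the visit day. The uncovered share of women's contraception time is (1 − s)(112 − v) / [(1 − s) × 112 + s × 14].
- s = 0: 75.0% (v = 28) or 68.8% (v = 35).
- s = 0.5: 42/63 = 66.7% (v = 28) or 38.5/63 = 61.1% (v = 35).

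The range is therefore about 61% to 75%. The exception reduces the gap without closing it.

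**The competing clauses side by side**
- Under 7.4.10.3, collection ends at day 28 to 35.
- Under 7.4.10.2 read with 16.4, the reporting duty lasts through extended follow-up, and the uncovered share is 0% for subjects still in it. Section 7.4.10.4 likewise covers a partner's pregnancy that begins while the subject is participating.
- Section 4 says that subjects who progress generally stop treatment and are taken off the study, although follow-up visits continue. A site could reasonably conclude that participation has ended for them.

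**Contacts already planned.** Section 4, footnote 58 and Section 16.3 schedule contacts or skin exams every 4 weeks or monthly (±7 days) for 6 months after treatment. Counting 4-weekly from day 28 gives days 56, 84 and 112 within the 16 weeks, with more contacts afterwards.

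**The case against.** The strongest reply is that the protocol already covers late pregnancies. Section 7.4.10.2 has no 28-day limit: any pregnancy during participation is reportable within 24 hours and followed to outcome, and Section 16.4 keeps participation and data collection going through extended follow-up. Adverse outcomes have further routes. Spontaneous abortion must be reported as a serious adverse event (7.4.10.2), and a congenital anomaly is one by definition (11.2). Treatment-related serious events are recorded up to any follow-up contact (11.7), and a pregnancy-associated serious event judged possibly related is reportable even after study completion (7.4.10.2).

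Much of this stands. A reader might infer that most at-risk pregnancies are not captured, or that fetal outcomes would be missed simply by following the plan. The documents support neither reading, given the clauses above. The 69% to 75% is also a share of calendar time. It becomes a share of pregnancies only if conception is assumed constant over the 16 weeks, and no rate or number of women of child-bearing potential is given.

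The reply does not remove the conflict. Section 7.4.10.3 is the specific clause on timing, and a site following it stops at day 28 to 35. The scope of participation is unclear after progression. The later routes depend on a serious event, in most cases one judged related, so an ongoing or uneventful late pregnancy has no sure path to the sponsor and no scheduled question that would find it.

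The practical weight is modest. Enrollment had closed, and by 06-Apr-2020, 55 of 206 subjects were still on treatment. For those 55 the post-treatment period still lay ahead.

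**Conclusion.** The point holds as an internal inconsistency with a definite size. The stated collection window ends 11 to 12 weeks before the 16-week contraception period does, leaving 69% to 75% of that time outside it (about 61% to 75% for women if up to half are assumed to end on dabrafenib monotherapy). It conflicts with the wider reporting duty in 7.4.10.2 and with 16.4. The supportable consequence is that late pregnancies without a serious adverse event judged related may go unreported at sites that follow 7.4.10.3.

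This rests on two things: reading 7.4.10.3 as governing the timing, which its title and wording invite, and treating the contraception period as the period over which pregnancies are of interest. The second is an inference from the teratogenicity text in Section 1.4; the protocol itself calls the 16 weeks only a contraception requirement. How many pregnancies would be affected cannot be derived from the documents.

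**What to change.** Reconcile Sections 7.4.10.2, 7.4.10.3, 7.4.10.4 and 9.1 so that one collection period is stated, for subjects and for partners, and covers at least the whole post-treatment period for which the protocol requires contraception. State that it applies regardless of progression or withdrawal from treatment, as long as the subject is being followed. The lead sentence of 9.1.1 and the two-part rule in 7.4.10.1 should be reconciled at the same time, so that the length of that period is unambiguous for women stopping dabrafenib monotherapy. This changes no contraception or dosing rule.

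Add a pregnancy question to the existing 4-weekly contacts in the first 6 months after treatment. These span the 16 weeks and run beyond them, so a pregnancy that begins late in the period can still come to light, and no new visit is needed.

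The cost is a short text change, one added question per contact, and a few more reports to process.
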